**Table 7: Intensity and duration of endurance training over 18 month RCT as determined by HRMax**

Month	Intensity (%HR max)	Min/session
1-2	50%	30
3-4	55%	35
5-8	60%	40
9-12	65%	40
13-16	65%	45
17-18	70%	45

## 7.2 Cognitive Interventions

Cognitive interventions in the My-AHA project will comprise working memory training (N-back task), cognitive bias modification therapy (CBMT). As with physical interventions, the type of cognitive intervention offered to each participant will be individually tailored as determined by their individual areas of strength and weakness identified at each assessment point.

### 7.2.1 *Working memory training (N-back task)*

The main target group for n-back training is healthy elderly individuals. To achieve maximum adherence, self-efficacy, and engagement the n-back task will use graded difficulty whereby task difficulty is continuously adjusted to match participant level of performance.

Two versions of the n-back task will be used: a letter-based and a visuospatial version. In the letter-based n-back task, letters are capitalised at 20% of the monitor height and appear in black Arial font on a white background in the centre of the screen. For the visuospatial n-back task a 3 by 3 blue grid (11.5 cm x 11.5 cm) is displayed on a white background size with a blue fixation cross is constantly visible in the centre slot. For the visuospatial n-back task, the stimulus is a blue square (3.5 cm x 3.5 cm) that appears in different positions inside the grid slots, except the centre position containing the fixation cross, hence 8 positions. For both letter-based and visuospatial n-back tasks, 8 combinations of presentation time (fixed 2000 ms; variable starting at 2000ms decreasing by 100 ms each successful block or increasing 100 ms each unsuccessful block; variable starting at 500 ms decreasing by 50 ms each successful block or increasing 50 ms each unsuccessful block) and inter-stimulus intervals (ITI; 0 ms or 2000 ms) will be used. Participants are instructed to respond by pressing a response key/button as to whether the letter currently on screen matches the letter presented n letters previously. The ratio of non-targets and targets is 2:1, presented in a random order. During a 'lure' trial the current stimulus matches the one  $n + 1$  or  $n - 1$  stimuli previously. Each block contains two lures (e.g., 2-back targets in a 3-back block), which constitutes 10% of all trials. Each block consists of  $20 + n$  trials, such that a 3-back block would comprise 23 letters with 20 possible pairs. Participants begin their first trial with  $n = 2$  (regardless of previous performances), while adjustments are continuously made, based on participants' performance. Upon a successful block (at least 90% correct responses)  $n$  increases by 1, upon a non-successful block (below 75%),  $n$  decreases by 1. The level of  $n$  is maintained when participants give between 75% and 89% correct responses. A session comprises 15 blocks of n-back training (approximately 15 to 20 minutes). Participants will be provided with real-time feedback following each relevant trial, which is done using a stop-light paradigm. Two small circles (1.5 cm diameter, arranged green above red) are placed in the bottom left corner of the screen. All size measurements are relative to a 17-inch screen. The feedback is triggered directly following a response or in the case of a 'miss' during the ITI. In case of a match, the green circle lights up for 200 milliseconds. If participants' response is incorrect (false positive, miss, or false negative) the red circle lights up for 200 milliseconds. At the end of the training session participants are provided with an overview of their performance, e.g.: correct hits, and misses, as well as average level of  $n$ . Au and colleagues  have reported a dose-dependent relationship between working memory training and positive outcomes. Reliable effects have been achieved using n-back training daily on weekdays for 20 days for 25 minutes (roughly 15 blocks). The training will be delivered via the My-AHA app directly (PC, Tablet or Mobile phone) but can also be installed on the participant's home computer and operated with a keyboard or computer mouse.

### 7.2.2 *Cognitive Bias Modification Therapy (CBMT)*

CBMT works by training anxious or depressed individuals to disengage from threat-related stimuli and redirecting their attention towards other ‘positive’ stimuli [20]. Such training has been found to lead to increased mood and lower stress reactivity [21, 22]. Essentially, during CBMT participants select ‘good’ or ‘positive’ options over ‘bad’ or ‘negative’ ones. By consciously selecting the ‘positive’ option repeatedly, the negative bias becomes overridden and, over time, replaced by a novel, more adaptive habit. There are two common variants of CBMT, namely ‘attention bias modification’ (ABM) and ‘interpretative bias modification’ (CBM-I), which both have been reported to be effective in reducing anxiety and depression pathology [23]. ABM will be used in the My-AHA intervention package. In ABM participants learn to direct their attention towards relatively positive stimulus, which can be a word or a picture, and away from threat-related stimuli.

ABM is a modified computerized visual-probe procedure in which a pair of stimuli of different valences (e.g. a happy and a sad face, happy and neutral face, or neutral and sad face) are presented simultaneously then followed by presentation of a probe (one or two dots) behind one of the stimuli. Stimuli are presented for either 500 or 1000 ms before the probe is displayed. Randomization is set such that 500 and 1000 ms trials occur at the same frequency throughout a session. The presentation of a one-dot or two-dot probe is also randomized. Participants are instructed to press a button according to the number of dots presented. The appearance of the dots is manipulated, such that the dots always appear in place of the more positive stimulus. Participants learn implicitly to direct attention towards the happy stimuli and away from the negative ones, which constitutes a shift in attentional bias. A session of ABM comprises 96 trials and participants are recommended to complete two sessions daily for 28 sessions in total.

### 7.3 Psychosocial Interventions

Three social interventions will be implemented in the My-AHA project: group activity interventions; group support interventions, and a social media platform.

Group activity interventions will increase participant engagement in social interaction by provision of targeted group based activities including: group physical activity classes, group cooking classes, and group excursion based activities (e.g., visiting a museum). The My-AHA platform will match participant's preferences for type of activity and will create digital activity groups for participants with common preferences. The My-AHA platform then matches appropriate group activity proposals and presents the demand for specific group activities to secondary stakeholders as providers of group activities.

Group support interventions will provide an opportunity for participants to find targeted help and support (e.g., bereavement support, disease support such as cancer support groups). My-AHA participants can set corresponding parameters in their profile to indicate their need for support. The My-AHA platform will match support groups to individual participants, based on the parameters and preferences set by the participant.

The social media platform will address technology literacy of elderly people and allow digital interaction with all My-AHA participants. The social media platform will encompass the exchange and sharing of information as well as communication with other participants. It will provide a digital space for participants to interact with each other and share information, opinions, recommendations, etc.

## 7.4 Nutritional Interventions

Nutritional interventions will be implemented using a nutrition application (**VitalinQ** - <https://www.vitalinq.nl/>) for mobile devices. The interventions to be deployed include: individual meal plan generation, and tailored nutritional advice and education.

### 7.4.1 *Meal plan generation*

With meal plan generation, users will be able to plan meals ahead. In My-AHA application, meal plans and recommendations will be generated and presented to the user. The application will check in the database which recommendations and preferences fit the profile. The recommendations are official guidelines, which have been determined by official nutritional institutions in every participating country. The preferences (such as known allergies, lifestyle (e.g. vegetarian) and/or kitchen type) can be entered into the profile by the user. These recommendations and preferences will be compared to the recipes in the database. The recommendation engine should be able to generate meal plans that fit the needs of each user, based on their user profile. The nutritional application will consider the anthropometric data, lifestyle, activity level, nutritional status of the user, and on user preferences in creating individually tailored meal plans. The application will generate plans for all different types of meals (breakfast, lunch, dinner and snacks), as well all meals for one day or all meals for one week.

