#### 4 Participant randomization

Participants will be randomized into 2 study arms, with 50% of participants allocated to each arm:

- Study Arm 1: Control group (n = 25)
- Study Arm 2: My-AHA intervention group (n = 25)

Randomization will occur at each study site independently.

Initial randomization of participants at each site will occur on a 1 (control) : 1 (intervention) ratio, with allocation of participants to each treatment arm being undertaken using an alternating allocation sequence based on order of entry into the study (i.e. participant 1 – study arm 1; participant 2 – study arm 2; participant 3 – study arm 1; participant 4 – study arm 2, and so on).

Once recruitment and allocation to study arms of 20 participants has occurred at each site. The study site PI will submit to the RCT Study Coordinator basic demographic information on the 20 participants recruited and allocated to study arms. The demographic information required for each of the 20 participants is:

- Gender
- Age
- Highest education level

The RCT study coordinator will review the balance of participants across study arms for these demographic variables within each study site and advise the Principal Investigator of any adjustment to the allocation procedures for remaining participant assignment to treatment arms to ensure equivalence of study arms within each site.

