## 7 My-AHA Interventions

The intervention in this study is defined as the My-AHA platform. Participants randomized into the intervention arm will have access to the full My-AHA intervention platform (see also Section 8 My-AHA User Platform interface). Participants in the control group will not have access to the intervention package (no treatment control). All participants recruited into the study have no active disease state being treated. All participants meet study criteria for pre-frail status, a non-clinical disease state.

The protocol in the intervention arm is designed to prevent deterioration from a non-clinical state (pre-frail) into the disease state (frail).

The no-intervention control arm will not receive any element of the My-AHA intervention, a no-intervention non-disease control group. Participants in both study arms undergo formal assessment of clinical frailty status at 4 timepoints (baseline, 6 mo, 12 mo, 18mo). **Development of clinical frailty is considered an adverse endpoint for the participant in this study.**

Where a control group participant displays evidence of clinical decline at 6 or 12mo assessment points (defined as meeting clinical criteria for frailty) they will be offered access to the My-AHA intervention suite. We cannot estimate or predict what proportion of the control participants may develop frailty during the 18 month trial as there is no published data on incidence, age-dependent prevalence, or on average rate of decline into frailty from pre-frail states.

Participants randomly allocated to the intervention group will be provided with access to tailored intervention packages. Intervention packages will target domains of pre-frailty (e.g. physical, social, cognitive, nutrition) identified at baseline assessment for each participant. The intervention packages will be revised following each assessment point to accommodate for changes in domain specific areas of pre-frailty.

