### 7.1.1 *Otago home-based exercise program (OEP)*

The OEP will be deployed as a home-based exercise programme used by older adults in their own homes without expert's supervision. Prior to commencing the OEP program each participant will have a home visit from an exercise instructor who will prescribe an individually tailored set of exercises according to the participant's clinical history and fitness level. The instructor will also provide each participant with detailed instructions regarding the correct implementation of each exercise. Participants will be provided with a booklet listing the exercises including short description and repetitions for each set as well as adjustable ankle cuff weights, which must be easy to take on and off. For participants, unable to exercise from a standing position, a chair-based exercise programme will be provided resistance-based training using ankle weights being replaced with resistance-bands.

Participants will undertake the OEP program one session per week, as each participant will engage in one additional group-based exercise session that targets the same domains as in the OEP. In addition, the OEP advice of undertaking a walking activity will be replaced with a recommendation of undertaking some form of endurance training for one additional session per week. This modified OEP program, including group exercise and endurance training, will result in a total of 3 hours of physical training per week.

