## My-AHA Demographic Questionnaire - BASELINE

### Demographic Information

Date of birth : DD / MM / YYYY

Age (years): \_\_\_\_\_

Gender: Male / Female *(circle one)*

Handedness Right / Left *(circle hand you write with)*

Height \_\_\_\_\_ cm

Weight \_\_\_\_\_ kg

Marital Status: Single / Married / Defacto / Widowed *(circle one)*

Describe your living situation

- Alone
- With a partner/spouse
- With children/grandchildren

Where do you live?

- Own home (house / apartment / unit)
- Residential village (e.g. retirement community)
- Supported accommodation (e.g. aged care facility)
- Nursing home

Are you currently living

- Independently with no support services
- Semi-independently – receive some support services (e.g. meals on wheels, cleaning support, etc)
- Fully dependent care (e.g. nursing home with meals and medical care provided)

Prior education history

A. \_\_\_\_\_ Total number of years at school (primary + high)

B. \_\_\_\_\_ Total number of years of post-school formal education  
(e.g. University/College)

C. \_\_\_\_\_ TOTAL EDUCATION YEARS (A+B)

Have you ever fallen over? Yes / No

If YES describe when and what occurred  
(e.g. injury) \_\_\_\_\_

\_\_\_\_\_

\_\_\_\_\_

\_\_\_\_\_

\_\_\_\_\_

How fearful are you of falling? 0 1 2 3 4 5

Never Rarely A little Moderately Often Always

Are you currently continent? Urinary Yes / No  
Bowel Yes / No

What type of events or entertainment have you undertaken in the last 2 months?  
(*tick all that apply*)

- Movies
- Plays / drama productions
- Pub / Club
- Concert / Recital
- Special Performances
- Dancing
- Visiting Friends
- Attending a sporting event
- Meal at a restaurant

How would you spend a typical day  
(*tick all that apply*)

- Sleep / nothing
- House work
- TV
- Radio
- Listening to music
- Walking
- Gardening
- Crosswords
- Pet care
- Socialising
- Reading
- Writing
- Studying
- Teaching
- Volunteering
- Paid work
- Strategy games (e.g. chess, bridge, cards)
- Helping friends/family
- Artistry (e.g. drawing, painting, sculpture, creative writing, acting, etc.)
- Prayer / religious activity
- Playing music
- Brain training games (on a computer, ipad etc)
- Learning something new
- Hobby or past-time
- Intellectual/professional

How often do you make an outing to see a family member,  
friend or a group of friends?

- Never
- Less than monthly
- Monthly
- Fortnightly
- Weekly
- Daily

Are you currently diagnosed with a medical condition? Yes / No

IF YES

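### Alternating allocation by order of entry always splits cohabiting partners who enrol consecutively, and nothing shown prevents or records exposure of the control partner to the home-based intervention

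*Protocol*

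**What the plan says.** **Allocation.** Section 4 states: "Initial randomization of participants at each site will occur on a 1 (control) : 1 (intervention) ratio". The method is "allocation of participants to each treatment arm being undertaken using an alternating allocation sequence based on order of entry into the study", starting with control. The arms are to hold 25 each. After 20 participants at a site, the coordinator reviews balance on gender, age and education and may adjust the procedure for the rest.

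**Home use.**
- Section 7.4.1, on the nutrition application: "The application will generate plans for all different types of meals (breakfast, lunch, dinner and snacks". Plans can cover a day or a week.
- Section 7.1.1, on the Otago programme done at home: "Participants will be provided with a booklet listing the exercises". Ankle cuff weights are supplied as well.
- Section 7.2.1 lets the n-back training be installed on the participant's "home computer and operated with a keyboard or computer mouse", as an alternative to the app.

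**Control condition.** Section 7: "The no-intervention control arm will not receive any element of the My-AHA intervention". The only planned exception is a control who progresses to frailty.

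**Setting and households.** Section 2.1 recruits 50 people from one region, living in their own homes, retirement communities or non-secure residential aged care. The baseline questionnaire (Appendix 5) offers "With a partner/spouse" as a living situation. Tables 1 and 3 and the screening checklist (Appendix 4) contain nothing on more than one participant per household. Neither demographic questionnaire (Appendices 5 and 6) asks whether a partner is enrolled.

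**The concern.** Partners who volunteer together may well be screened on the same occasion and so enter one after the other. That is an inference, but Section 6.6.2 makes it practicable by allowing assessment visits at the participant's residence. For such a couple, alternation gives the worst outcome available: one partner is always a control and the other always receives the intervention in the same home.

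The control partner may then eat the planned meals or use the booklet and weights. A control who takes up part of an effective intervention moves towards the intervention arm, so the between-arm difference shrinks on the outcomes affected. Adherence is logged through the platform (Section 6.3), which would not show informal use by a control. The screening and demographic forms do not identify enrolled household members. The exposure therefore could not be found later from those forms, nor explored in a sensitivity analysis based on them.

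**Working it through.** **1. Arm sizes under the stated rule.** Odd entries go to control and even entries to intervention. Fifty entries give 25 and 25, as Section 4 states. The first 20 give 10 and 10.

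**2. Chance that two consecutive entrants are in opposite arms.**

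| Method | Calculation | Result |
|---|---|---|
| Alternation (Section 4) | 49 of 49 adjacent pairs | 100% |
| Permuted blocks of 4 | (37 × 2/3 + 12 × 1/2) / 49 | about 63% |
| Random 25/25 list | 25/49 | 51% |
| Simple 1:1 randomisation | 1/2 | 50% |
| Household allocated as one unit | by construction | 0% |

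In the blocks-of-4 row, 37 adjacent pairs lie within a block and 12 straddle two blocks.

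**3. Partners who do not enter consecutively.** For two positions taken at random from the alternating sequence, the chance of opposite arms is (2 × 25 × 25) / (50 × 49) = 1250/2450 = 51%. This equals the figure for a random list. The excess caused by alternation is confined to close, in particular consecutive, entry.

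**4. What dilution would do.** The protocol states no effect size, alpha or power, so everything here except 25 per arm is assumed: two-sided alpha 0.05, 80% power, SD 1, normal approximation, no dropout.

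- Detectable difference: d = (1.960 + 0.842) × √(2/25) = 0.79 SD.
- If k of 25 controls pick up a share s of the effect, the expected difference becomes d × (1 − s × k/25).
- Power = Φ(d × (1 − s × k/25) × √(25/2) − 1.960).

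| Exposed controls (k) | Difference lost, s = 0.5 | Power | Difference lost, s = 1 | Power |
|---|---|---|---|---|
| 0 | 0% | 80% | 0% | 80% |
| 1 | 2% | 78% | 4% | 77% |
| 2 | 4% | 77% | 8% | 73% |
| 3 | 6% | 75% | 12% | 69% |
| 5 | 10% | 71% | 20% | 61% |

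Each exposed control implies one split couple, so k = 5 would mean that 10 of the 50 participants belong to split couples. The documents support no particular k or s.

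**The case against.** **Sharing is not stated.** A reader might infer that control partners will in fact share the meals, software and exercise material. The documents do not say so. They do not say that couples will enrol; a response option on a general questionnaire is weak evidence of joint enrolment. Each partner must also separately meet one or two physical frailty criteria, reach the HVLT threshold and pass a long list of exclusions, so eligible couples may be few. This stands, and it is why the point is put as a possibility.

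**Much of the intervention is personal.** Packages follow each person's own deficits (Section 7), meal plans follow the user's profile (Section 7.4.1), platform login is password-secured (Section 8), and FAME is a supervised class (Section 7.1.2). This stands for the platform and weakens the software route, leaving mainly the optional home-computer installation. It does not stop partners eating the same dinner or using the same booklet and weights. It does mean that the same loss should not be presumed for every outcome.

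**The protocol does not contradict itself.** One might read Section 7's statement about controls as made untrue by a shared household. It describes what the trial provides to controls, and a shared meal does not falsify it.

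**The size is not known.** Taking 10–40% of controls as living with an intervention participant, each picking up 25–75% of the effect, gives a dilution of 2.5–30%. Every input to that range is assumed. Its upper end needs 10 split couples, or 20 of the 50 participants. It cannot be offered as an estimate, and the claim that a few pairs would change the result is not shown.

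**It may be covered elsewhere.** The consent forms are not available, and a statement on households there cannot be excluded. Eligibility and allocation rules, however, belong in Sections 3 and 4, which are available and silent on this.

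**Conclusion.** The concern holds in limited form. Section 4 splits consecutive entrants with certainty for the first 20 at a site, and afterwards unless the procedure is adjusted. For cohabiting partners this opens a route to contamination through material used at home, and the eligibility, allocation and screening text shown neither prevents nor records it. Any such exposure to an effective component pulls the comparison towards no difference.

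The size cannot be determined. On the stated assumptions, one to three half-exposed controls cost about 2 to 5 percentage points of power (80% to 78–75%), and three fully exposed controls about 11 points (80% to 69%). If no couples enrol, there is no loss. The case for acting rests on the low cost of the change and on the difficulty of identifying the exposure afterwards, and not on a demonstrated large bias.

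**What to change.** - **Section 4:** allocate members of one household together as a single unit. Alternatively, in **Table 1**, admit one participant per household.
- **Appendix 4:** add a screening item asking whether a household member is already enrolled.
- **Analysis:** if pairs are kept together, allow for the correlation within pairs.

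The cost is one sentence and one screening item. Under household allocation, arm sizes may differ by one or two and a few pairs will be correlated. Under the one-per-household rule, a few second household members are turned away. Neither option deals with contact between neighbours in a retirement community, or with the predictability of an alternating sequence, which is a separate matter.
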